#### Table 10. Subgroup Analysis

Dependent Variable(s)	Statistical Test
	Logistic Regression
Occurrence of one or more SAE (Yes/No)	Independent variables: Treatment, Subgroup, Treatment*Subgroup Interaction
Occurrence of one or more Device-Related AE (Yes/No)	Logistic Regression Independent variables: Treatment, Subgroup, Treatment*Subgroup Interaction
Rescue Medication Use for Index Knee OA Pain (Yes/No)	Logistic Regression Independent variables: Treatment, Subgroup, Treatment*Subgroup Interaction

# 5. Safety Endpoints

During Phase I, all Adverse Events will be collected regardless of relationship to the device. During Phase II, only AEs that are potentially related to the device/procedure will be collected.

Adverse events will be designated in MedDRA categories by a qualified reviewer that is blinded with respect to treatment assignment. Specific adverse events are expected to occur at low frequencies, and therefore no significant differences between groups are expected. Accordingly, the *a priori* tests planned will determine whether the overall rate of adverse events differs between treatment groups, and whether differences between groups exist with respect to device relatedness and severity. Results for each category will be tabulated by treatment group. In this tabulation the number of subjects with one or more adverse events fitting into an individual adverse event (AE) category will be displayed beside the count of subjects with no AEs fitting into that category. A Fisher's Exact test will be performed to determine whether treatment groups differ. In addition, the number of AEs and the corresponding percentage of total AEs within each category of severity and relatedness to the device will be summarized by treatment. A listing of all AEs will be provided, and a narrative of each serious AE will be generated.

In addition, a time-course distribution of adverse events will be created based on contiguous intervals between planned visits, as shown in *Table 11*, *Table 12*, *Table 13*, and *Table 14*. In this table, one AE per subject, category, and time interval will be counted.

	Injection	1 Month	3 Month	6 Month	12 Month
Interval	Injection to Day 15	Day 16 to Day 61	Day 62 to Day 137	Day 138 to Day 274	Day 275 to Day 547
AEs					
AE Type 1					
AE Type 2					
Serious AE					
AE Type 1					
AE Type 2					
Device Related AE					
AE Type 1					
AE Type 2					

Table 11. Time Course Distribution of AEs - APS

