	Anatomical changes will be evaluated by radiographs (X-ray). In the long-term follow-up phase $(12 - 60 \text{ months})$, the study will evaluate treatment durability, patient preferences, and treatment cost effectiveness over time. During this long-term follow-up period, safety will be assessed by tracking the occurrence of AEs of interest only.

Du	uring screening, potential subjects who provide informed consent
wi	Il be assessed for eligibility. Screening will consist of meeting all
in	clusion and exclusion criteria, including a WOMAC LK 3.1 pain
su	bscale score \geq 9 and \leq 19 and by providing objective
ph	siological evidence of OA using the Kellgren-Lawrence (K-L)
sc	ale (assessed from radiographs). Subjects will also provide
de	emographic and medication use information. Baseline X-ray ¹ and
ar	MRI ² will be collected.
W	ithin 28 days of the screening visit, subjects will return to the clinic
fo	r treatment. Subjects will complete the baseline outcomes
m	easurements including the EuroQol questionnaire (EQ-5D), and
N	umeric Rating Scale (NRS) for knee pain. The WOMAC score
re	corded at the screening visit will serve as the baseline (pre-
inj	ection) WOMAC score, and the WOMAC questionnaire will not
be	ere-administered prior to treatment.
Ar	n injection visit occurring between 28 and 32 days after the
sc	reening visit will be considered a minor protocol deviation. In the
ev	ent that the injection procedure cannot be completed within 32
da	iys of the screening visit, the subject will be screen-failed, but is
eli	gible for immediate re-screening. The re-screening and injection
vis	sits can be combined, as long as the subject still qualifies per all

¹ Radiographs up to 24 months of follow-up will be sent to a core imaging laboratory for assessment of eligibility and therefore must always be performed following the criteria set in the Imaging Review Charter from Core Imaging Laboratory.

² Baseline MRIs will not be sent to a Core Imaging Laboratory and should be performed only after subject meets all other eligibility criteria. Also, previously taken MRI may be used if obtained up to 90 days prior to study treatment. Furthermore, in the event that an otherwise eligible subject is unable to undergo the MRI procedure due to significant safety risk (i.e. subject has pacemaker, documented diagnosis of claustrophobia, etc.), MRI does not need to be performed and this will be not be documented as a protocol deviation

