An X-ray will be obtained at 12 months and annually thereafter to assess anatomical changes. Only radiograph images taken up to 24 months of follow-up will be transferred to the Core Imaging Laboratory for independent review. Image acquisition, transfer, and analysis procedures will be performed using validated, prospectively defined methods. All AEs that occur during the 12 month blinded study period will be recorded. In the long-term follow-up phase (12 - 60 months), only events of interest will be recorded.

After each subject completes all 12-month follow-up evaluations, only subjects will be blinded to the individual treatment allocation resulting in single-blind design following 12-month follow-up time point. Subjects from both groups will be able to request additional injections of their originally assigned treatment as frequently⁴ as needed, provided they did not experience any significant clinical concerns after previous treatment administrations and are benefiting from it, as determined by the investigator. During the long-term follow-up phase (12 - 60 months), subjects may also elect to cross over to the other treatment arm and receive additional injections of the other treatment as frequently as needed, provided they did not experience any significant clinical concerns after previous treatment administrations and are benefiting from it, as determined by the investigator. Subjects may only cross over from their originally assigned treatment group to the other treatment group one time during the study. Subjects seeking alternative invasive OA treatment in the index knee who do not wish to cross over or who have already crossed over will exit the study, and their selected treatment option will be recorded.

⁴ Please refer to Synvisc One IFU for specified clinical use requirements.

Study Duration:	Maximum study duration per subject is 62 months: 60 r	nonths from
	treatment to last follow-up, and two additional mo	onths if the
	maximum visit window time is realized.	
Inclusion Criteria:	1. Male or female at least 18 years of age at time of	f screening.
	2. Willingness and ability to comply with study proc	cedures and
	visit schedules and able to follow oral a	and written
	instructions.	
	3. A standing knee radiograph showing a K-L gra	de of 2 to 4
	and an absence of severe osteoarthritis	defined as
	advanced stage osteoarthritis, including large o	steophytes,
	chronic fractures or bone remodeling, severe	deformity or

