arm (i.e. patients with clinically meaningful improvement in
WOMAC Pain score, inclusive of originally assigned and cross-
over patients)
 Average number of cumulative interventions per patient
• Time from the initial injection (nSTRIDE APS or HA) to
subsequent injection(s), cross-over, or study exit for other
invasive treatment
 Resource utilization for index knee OA.

⁶ Clinically meaningful improvement is considered to be an improvement of at least 20% from baseline

	The following endpoint will be assessed annually in the long-term
	follow-up phase for patients that have crossed over:
	Percentage of patients preferring each treatment due to:
	1. Greater pain relief
	2. Longer lasting pain relief
	3. Greater improvement in function
	4. Longer lasting improvement in function
	5. Fewer post-injection side effects
Safety Endpoints	Occurrence of all AEs up to 12 month time-point and
	occurrence of AEs of interest across all post-operative time
	points

This Clinical Investigation Plan is written in accordance with ISO14155:2011 "Clinical Investigation of medical devices for human subjects – Good clinical practice" (40). The Adverse Events sections is written in accordance with the ISO14155:2020 "Clinical Investigation of medical devices for human subjects – Good clinical practice" (41).

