### Table 13 - Time Course Distribution of AEs – Post-Crossover APS to HA

	2 nd Injection	1 Month	3 Month	6 Month	12 Month
Interval	Injection to Day 15	Day 16 to Day 61	Day 62 to Day 137	Day 138 to Day 274	Day 275 to Day 547
AEs					
AE Type 1					
AE Type 2					
Serious AE					
AE Type 1					
AE Type 2					
Device Related AE					
AE Type 1					
AE Type 2					

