# 7. Data Collection Time Points

Data will be collected at the screening visit, the injection visit, and at 1, 3, 6 and 12 months following the injection. After each subject completes all 12 month follow-up evaluations (Phase I), individual treatment allocation will be unblinded to the investigators. From this time-point on, only subjects will be blinded to study treatments resulting in a single-blind design during the longterm follow-up period (Phase II). During Phase II of the study, the subject may opt to get additional injections of their originally assigned treatment, or they may opt to crossover to the other treatment group and may receive multiple injections of the crossover treatment. Subjects may only crossover one time during the study. In Phase II, follow-up visits will occur at six month intervals until five years following the initial injection.

The follow-up visits will preferably be completed during an office visit to ensure subject compliance, but this is not mandatory and follow-up visits may consist of a structured telephone interview or electronic self-report with exception of annual visits at which radiograph is to be taken. The investigative center will contact the subject to complete the Follow-up and AE forms. The subject will be asked to complete a Patient Questionnaire.

A table showing the data collected at each time interval is presented in the study protocol.

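### The SAP collects Phase II adverse events by relatedness while the protocol collects AEs of interest; the SAP plans no AEs-of-interest analysis, and Tables 11-14 put filtered and full counts under the same labels

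*SAP*

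**What the plan says.** The two documents agree on Phase I. SAP section 5 states "During Phase I, all Adverse Events will be collected regardless of relationship to the device", and the protocol synopsis likewise records every AE during the 12-month blinded period.

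They differ on Phase II:

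- SAP section 5: "During Phase II, only AEs that are potentially related to the device/procedure will be collected".
- Protocol synopsis, Study Design and Procedures: "During this long-term follow-up period, safety will be assessed by tracking the occurrence of AEs of interest only", and later "In the long-term follow-up phase (12 - 60 months), only events of interest will be recorded".
- Protocol synopsis, Safety Endpoints: all AEs to month 12, together with "occurrence of AEs of interest across all post-operative time" points.

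On blinding, SAP section 7 says that after each subject's 12-month evaluations "individual treatment allocation will be unblinded to the investigators"; subjects stay blinded. Both documents allow crossover only in months 12-60.

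SAP section 5 plans four time-course tables. Tables 11 and 12 cover APS and HA from the first injection. Table 13 ("Time Course Distribution of AEs – Post-Crossover APS to HA") and Table 14 (the reverse crossover) count from the second injection. All four have the same rows (AEs, Serious AE, Device Related AE) and the same last interval, days 275 to 547.

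**The concern.** The protocol's criterion, as worded, is about which events matter. The SAP's criterion is about attribution. Neither document says that the two are equivalent, and the SAP has no analysis under the protocol's term.

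A relatedness criterion used at entry also differs in kind from relatedness recorded on a form. If it is recorded, the analyst can report results with and without unrelated events. If it decides entry, events judged unrelated are absent and no later analysis can restore them. In Phase II that decision falls in a period when investigators know the treatment, so expectations about either product could influence what is counted.

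The tables do not show the change of rule. A reader who sees a Serious AE row in Table 11 and another in Table 13 will take them to mean the same thing. At stake are the long-term and post-crossover safety comparisons. The double-blind data up to each subject's 12-month visit are not affected.

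**Working it through.** The plan gives no event rate or other figure to reproduce here. The check compares the rules and then applies day arithmetic to the SAP's own intervals.

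**1. Collection rule by phase**

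| Period | Protocol synopsis | SAP section 5 | Investigators |
|---|---|---|---|
| To the 12-month visit | All AEs | All AEs | Blinded |
| Months 12-60 | AEs of interest | Potentially related AEs | Unblinded |

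Phase II is 60 - 12 = 48 of 60 months, or 80% of planned follow-up.

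**2. Who applies the filter.** The only AE step stated to be blinded is MedDRA categorisation (SAP section 5), which acts on events already collected. SAP section 7 has the investigative center complete the AE forms. The natural inference is that unblinded site staff judge relatedness, but neither document names the assessor.

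**3. Tables 13-14.** Crossover happens only after month 12, so every day in these tables lies in Phase II. Under the SAP rule, all three row groups can contain only potentially related events. For the same true risk, and if any AEs at all are unrelated, the AEs row must be lower than under full collection. The same holds for the Serious AE row if any serious events are unrelated. The direction follows from the rule; the size does not.

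**4. Tables 11-12, 12 Month column.** Its length is 547 - 275 + 1 = 273 days. The rule changes at each subject's 12-month visit, so the filtered part depends on the date of that visit. The limits come from SAP Table 2.

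| 12-month visit on day | Days after the visit | Share of 273 |
|---|---|---|
| 365 (nominal) | 547 - 365 = 182 | 67% |
| 393 (end of in-window range) | 547 - 393 = 154 | 56% |
| 456 (end of widest window) | 547 - 456 = 91 | 33% |

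So the column mixes the two rules even for a visit on the last day of the SAP's widest 12-month window.

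**5. Reach of the tables.** Month 60 is day 60 × 365.25/12 = 1826, so Phase II runs about 1826 - 365 = 1461 days. For a subject who never crosses over, Tables 11-12 cover 182/1461 = 12% of it. No time-course table is planned for later AEs or for those after repeat injections of the assigned product. The text after Table 14 promises AE tabulation for the Phase I intervals only. The Fisher's exact comparison in section 5 and the SAE and device-related AE models in Table 10 do not name a phase, so they could pool the two rules. The planned AE listing is not a comparative analysis.

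**The case against.** The strongest objection is that the mismatch may be one of words only. The available protocol text does not define AEs of interest, and it refers to a fuller treatment elsewhere: "The Adverse Events sections is written in accordance with the ISO14155:2020". If that section defines events of interest as potentially device- or procedure-related, the two rules coincide. SAP section 7 also refers to the protocol for what is collected at each interval, so sites following the protocol would record events of interest whatever SAP section 5 says. This stands. A reader might infer that the protocol's safety endpoint will not be delivered, or that the two rules must select different events. The documents support neither claim. Nor does the available text show that the protocol selects events by type regardless of relatedness.

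Several smaller objections have force:

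- Unblinded assessment of relatedness is inferred, and the subjects who report symptoms remain blinded.
- The protocol itself restricts Phase II collection, so restriction is a design choice and Tables 13-14 would differ from full Phase I capture under either rule.
- No test of Tables 13-14 against Tables 11-12 is planned. Such a comparison would be confounded anyway, because crossover is elective and limited to subjects without significant clinical concerns after earlier injections.
- It is tempting to conclude that a second injection will look safer than the first. Tables 13-14 cover crossover only, not repeat injections of the same product.
- The Device Related AE row stays broadly comparable across phases.
- SAP section 1 treats the long-term follow-up endpoints as exploratory.

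These points limit the finding but do not remove it. Even if the definitions coincide, entry would still depend on attribution after unblinding, identical labels would still cover different content, and no analysis of the endpoint through month 60 would be specified.

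**Conclusion.** The concern holds in a limited form. The SAP's Phase II collection rule does not match the wording of the protocol's rule and endpoint, and the SAP plans no AEs-of-interest analysis. Followed as written, the SAP would understate AE and SAE rates after month 12 relative to Phase I under unchanged row labels. This affects all of Tables 13-14 and, with the visit on day 365, 182 of the 273 days (67%) in the last column of Tables 11-12; the share is 33% if the visit falls on day 456.

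These shares measure time, not events. The documents give no event rates or attribution rates, so neither the number of events lost nor any bias between arms can be estimated. The conclusion assumes that SAP section 5 is applied literally. The point about unblinded judgement also assumes that site staff assess relatedness. Whether the protocol's endpoint is lost remains open until the definition of AEs of interest is checked. Phase I safety up to the 12-month visit is sound on this point.

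**What to change.** 1. Reconcile the Phase II sentence in SAP section 5 with AEs of interest as the protocol defines them, and state that definition in the SAP. For those events, record relatedness as an attribute and do not use it as the entry criterion, unless the protocol's definition is itself based on relatedness. Name the relatedness assessor and that person's blinding status.
2. Add one table of AEs of interest by treatment, with the same definition in both phases, through month 60.
3. End the all-AE column of Tables 11-12 at each subject's 12-month visit. In Tables 13-14, relabel or drop the AEs and Serious AE rows so that they match what is collected. Compare phases only on event types collected in both.

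The cost is SAP wording, one extra table and possibly some additional Phase II events for sites to record. It is best done early, because events that were never collected are hard to recover later.

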Secondary objectives of this study include determining whether nSTRIDE APS is superior to HA in improving WOMAC LK 3.1 function at 12 months (as evaluated using the percentage of subjects showing at least the minimal clinically important difference (MCID)), and WOMAC LK 3.1 pain at 12 months (as evaluated using the percentage of subjects showing at least the minimal clinically important difference (MCID)), OMERACT-OARSI responder rates at 12 months, analyzing WOMAC pain and function in only the KL-II Subgroup at 12 months, evaluating superiority of APS over HA in improving Numeric Rating Scale (NRS) pain at 12 months, assessment of the changes in WOMAC Pain scores over time (baseline through 12 months), and evaluation of the usage of rescue medication within 12 months. These will be tested in a fixed sequential order pending the rejection of the primary null hypothesis.

Exploratory objectives of this study include determining whether APS is superior to HA with regards to improvement in mean EQ-5D outcomes (12 months minus baseline) and repeated measures of WOMAC Function, WOMAC stiffness, and total WOMAC score. In addition, changes in joint morphology (determined with X-ray images) will be evaluated. Subgroup analyses will be conducted to investigate whether the treatment effect varies depending on subjects' initial pain and baseline information. Analysis of exploratory endpoints will be done using alpha=0.05 with no adjustment for multiple comparisons.

A long-term follow-up phase will examine the superiority of nSTRIDE APS in the duration of the treatment effect, injection frequency, patient preferences, healthcare resource utilization, and associated costs. These endpoints will be treated as exploratory endpoints and analyses will be conducted using alpha = 0.05 with no adjustment for multiple comparisons.

Finally, the safety profile of nSTRIDE APS will be compared to HA by comparing adverse events and rates between treatment groups.

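### The safety comparison rests on Fisher's exact test with no effect estimate or interval, severity and relatedness lack a clear subject-level display, and the AE time-course tables have no number at risk

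*SAP*

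**What the plan says.** SAP Section 1 sets the safety aim as "comparing adverse events and rates between treatment groups". Section 5 carries it out in three displays.

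- **Subject-level table by arm.** It shows "the number of subjects with one or more adverse events fitting into an individual adverse event (AE) category" "beside the count of subjects with no AEs fitting into that category". The test is stated in one sentence: "A Fisher's Exact test will be performed to determine whether treatment groups differ". The a priori tests are said to address the overall AE rate and "whether differences between groups exist with respect to device relatedness and severity". The same paragraph says: "Specific adverse events are expected to occur at low frequencies, and therefore no significant differences between groups are expected".
- **Supplementary event-level summary by arm.** It gives "the number of AEs and the corresponding percentage of total AEs within each category of severity and relatedness to the device".
- **Time-course Tables 11 to 14.** These cover APS, HA, post-crossover APS to HA, and post-crossover HA to APS. The counting rule is: "In this table, one AE per subject, category, and time interval will be counted". No number at risk or person-time is specified.

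A listing of all AEs and a narrative for each serious AE are also planned. Table 10 in Section 4.7 adds exploratory logistic models, with treatment, subgroup and interaction terms, for at least one SAE and at least one device-related AE. Nowhere does the SAP specify a risk difference, risk ratio, confidence interval or exposure-adjusted rate for AEs. Table 7 in Section 4.5 expects significantly more HA than APS subjects to cross over.

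**The concern.** There are three linked gaps in what the safety results can show.

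1. **No estimate or interval.** The trial is sized on WOMAC pain, so tests on uncommon AEs have little power. A p-value does not say how large an excess remains compatible with the data, and that is what a safety comparison needs to report.

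2. **Severity and relatedness.** The only display explicitly laid out by severity and relatedness uses a denominator that treatment can change. Extra mild or unrelated events lower an arm's severe or related percentage with no fall in severe or related events. The subject-level table would solve this, but its category wording follows the sentence on MedDRA coding, and the SAP does not say that the table is repeated by severity and relatedness. The gap is clearest for severity, because Table 10 models serious and device-related AEs but not severe ones.

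3. **Time course without denominators.** A cell count cannot be read as a risk without the number of subjects it came from. In Tables 11 and 12 a reader can fall back on roughly equal randomized arms. In Tables 13 and 14 the groups are whoever chose to cross over, so there is no such fallback.

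**Working it through.** The SAP states no AE rate and no safety power, so there is no planned figure to reproduce. The event counts and risks below are assumptions for illustration.

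**Inputs.** 123 per arm (SAP 6.1); 1:1 allocation (SAP 1.3); interval bounds from Tables 11 to 14; two-sided 0.05 level (assumed, since Section 5 gives none).

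**Step 1: power of Fisher's exact test.** Power is the sum over all pairs (i, j) of Bin(i; 123, p1) × Bin(j; 123, p2), taken over pairs with Fisher p ≤ 0.05.

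| True risks | Power |
|---|---|
| 4% vs 8% | 17% |
| 5% vs 10% | 23% |
| 10% vs 20% | 53% |
| 5% vs 15% | 69% |

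A doubling from 5% would be missed about three times in four.

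**Step 2: what an interval adds.** Take 10 of 123 versus 5 of 123 subjects. The risks are 8.13% and 4.07%, a difference of 4.07 points (5/123). The Wilson 95% limits are 4.48 to 14.32 and 1.75 to 9.16. Newcombe's interval for the difference is:

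- Lower: 4.07 - √[(8.13 - 4.48)² + (9.16 - 4.07)²] = 4.07 - 6.27 = -2.2 points.
- Upper: 4.07 + √[(14.32 - 8.13)² + (4.07 - 1.75)²] = 4.07 + 6.61 = +10.7 points.

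Fisher's p is 0.29. The p-value says only that the result is not significant. The interval says that an excess of up to about 11 points is not excluded.

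**Step 3: share of AEs against subject risk.** Suppose 20 severe of 200 AEs in one arm and 12 of 80 in the other, each severe AE in a different subject.

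- Share of AEs: 20/200 = 10.0% versus 12/80 = 15.0%.
- Subject risk: 20/123 = 16.3% versus 12/123 = 9.8%; difference +6.5 points (Newcombe 95% CI -2.0 to +15.1), Fisher p = 0.18.

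The percentage column and the subject risk point in opposite directions. The event counts, 20 and 12, would be printed beside the percentages.

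**Step 4: time-course tables.** Interval lengths (end - start + 1) are 15 days (16 if day 0 counts), 46, 76, 137 and 273. Ten subjects with an event among 123 at risk, without dropout, correspond to 10/(123 × 15) = 5.4 per 1,000 subject-days in the first interval and 10/(123 × 273) = 0.30 in the last. Reading along a row therefore needs person-time.

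For Tables 13 and 14, let the crossover groups have sizes m1 (APS to HA) and m2 (HA to APS) and the same risk r in an interval. The expected cells are r × m1 and r × m2, so their ratio is m1/m2 whatever the risk. If m2 exceeds m1, as Table 7 expects, Table 14 shows more AEs after crossover to APS at equal risk. Without m1 and m2 the reader cannot correct for this.

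**The case against.** The strongest reply is that the event-share summary is a supplement. The subject-level table comes first and prints both counts, the a priori tests are said to cover relatedness and severity, and all AEs are listed. That stands, and it rules out several stronger inferences.

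- **That an arm with more severe events would look safer overall.** The documents do not support this. The number of AEs is printed beside each percentage, and the planned arms are equal. Only the percentage column can mislead.
- **That unequal intervals bias APS against HA.** Tables 11 and 12 use identical bounds, so interval length alone cannot favour an arm. It distorts only the trend within a table.
- **That the short first interval hides an early excess.** A separate column from injection to day 15 isolates early events, and the arms can be compared in that cell.
- **That the counts would rise about 14-fold with no change in risk.** With a constant hazard of ln 2/365 per day (50% with an AE in 12 months), 123 × (1 - exp(-hazard × days)) gives 3.5 subjects in the first interval and 49.8 over the full last one. But Section 5 restricts AE collection in Phase II to potentially device- or procedure-related events. All-AE collection over days 275 to 365 (91 days) gives about 19.5, roughly 6-fold.

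It is also fair that no passage says non-significance will be taken as similar safety, that the sentence on expected non-significance concerns specific rare AEs, and that an interval does not raise power. The interval does show how much remains unexcluded, which the p-value does not. Table 10 does not fill the gap: its models are exploratory, carry an interaction term, omit severity, and come with no stated plan to report a treatment odds ratio or its interval.

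**Conclusion.** The point holds as a gap in estimation and reporting, not as a demonstrated bias towards either arm. Section 5 commits to a test with about 17% to 23% power for a doubling from 4% or 5%, and to no estimate or interval. In the 10 versus 5 example, p = 0.29 coexists with an interval of -2.2 to +10.7 points. Severity has no unambiguous subject-level display. Tables 11 to 14 lack denominators, and the consequence is greatest in Tables 13 and 14, where group sizes are self-selected and the SAP itself expects them to differ.

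The figures assume 123 analysed per arm, a two-sided 0.05 level, and invented event counts and risks. Other risks would change the numbers, but not the absence of an estimate. The primary efficacy analysis is unaffected.

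**What to change.** Amend SAP Section 5 as follows.

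1. State that the subject-level table is produced by severity and by device-relatedness, as n/N (%) of subjects with at least one such AE in each arm. The share-of-AEs summary may stay as a supplement.
2. Give the APS minus HA risk difference with a 95% confidence interval (Newcombe, for example) for any AE, SAE, severe AE and device-related AE. Base the safety statement on these intervals, with Fisher's p-value as supporting information.
3. Add the number at risk and the person-time for each interval to Tables 11 to 14, with the size of each crossover group at the head of Tables 13 and 14. In Tables 11 and 12, the column for days 275 to 547 spans the change in collection rule after 12 months, so its person-time should be split at that point or the change footnoted.

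The cost is minor programming and SAP wording; no new data are needed. The drawback is that the intervals will be wide and will show how little can be excluded at this sample size.
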